## **Study Protocol**

**Study design:** Prospective, randomized, controlled, double-blinded study with three treatment arms.

**Sample size:** 150 teeth with deep caries of subjects willing and able to return to UIC COD for recall purposes.

**Eligibility criteria:** Subject must meet the inclusion criteria to participate in the study.

**Clinical inclusion criteria:**

- Adults in good general health between 18 and 64 years of age;
- Active carious lesions deep into dentin (75% or more of dentin) involving occlusal/incisal and/or proximal surfaces of permanent teeth;
- Absence of clinical symptoms of irreversible pulpitis (spontaneous pain);
- Absence of periapical pathology, sinus tract, swelling or abnormal mobility;
- Restorable teeth.

**Radiographic inclusion criteria:**

- Extension of carious lesion close to potential exposure upon excavation (within the D3 region – lesion extending 2/3 within dentin); with the presence of a well-defined radiodense zone between the lesion and the pulp.
- Absence of periapical radiolucency;
- Absence of thickening of the periodontal ligament PDL;
- Absence of resorptive defects;

**Exclusion criteria:**

- Non restorable teeth;
- Teeth with:
  - Recent trauma (within 6 months);
  - Calcified root canals;
  - Periapical radiolucency;
- Patients experiencing spontaneous moderate to severe pain;
- Patients that are pregnant or planning to become pregnant in the next year.
- Patients taking analgesics, anti-inflammatory, or antidepressant medications;
- Patients with orthodontic treatment;
- Newly erupted teeth.

## **Subject management and recruitment process**

Recruitment flyers (attachment #1) will be posted in different locations at the University of Illinois at Chicago campus.

Recruitment e-mails and messages will be sent to all the faculty and students attending predoctoral and postdoctoral clinics at UIC College of Dentistry. We will also send recruitment messages to all faculty, staff and students at the University of Illinois at Chicago using campus wide massmail listservs. In addition, medical records will be reviewed to determine subject eligibility.

Those subjects who will volunteer to participate will be asked to contact via phone the principle investigator or study coordinator, to comply with the inform consent process (attachment #3 – phone call script).

Once patients have been properly screened and approved for the study, the selection of the treatment that they will receive will be carried out randomly, using random integer generator ([www.random.org/integers/](http://www.random.org/integers/)). Teeth of subjects will be first stratified into those needing indirect pulp capping and direct pulp capping. Based on stratification, subjects will be randomized to one of three arms (indirect pulp capping) or one of two arms (direct pulp capping). Patients will be blinded to the treatment.

Subjects will be compensated in cash for their participation in the study.

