### **Study schedule:**

The principle investigator or study coordinator will be the initial contact. Potential subjects will be approved for screening through a brief interview and intraoral examination.

- **Screening appointment:** A screening appointment will be scheduled and potential subjects will be approved after a thorough interview and intraoral and x-ray examinations. Each subject will be provided with a written consent form to read and attest with his or her signature. Patients will be assured of the privacy of their data and will receive a 3 digit number ID. All data collected will be saved in password protected computer in the principal investigator office, room 531A (key access only). The screening process will include medical and dental history, demographics, current/concomitant medication, oral soft and hard tissue examination, and a review of all inclusion and exclusion criteria (attachment # 5 and 6). Pregnancy test will be provided to childbearing women subjects at screening appointment to rule out pregnancy (to meet inclusion/exclusion criteria). The pregnancy test to be provided is First Response Pregnancy Test Stick (Church & Dwight Co. Inc).
- Subjects who are found eligible through the screening process will be evaluated preoperatively through a periapical and bitewing radiographs (**Figure 1**). The penetration of the lesion will be assessed in the bitewing radiograph according to the inclusion criteria. To obtain period-identical x-rays, a specific film holder (Super-bite; Kerr) Rinn XCP film holder will be used. An acrylic resin (Duralay) pattern will be fabricated for each subject on the biteblock of the film holder to be able to reposition it when taking follow up radiographs. Also baseline pain assessment will be recorded via visual analogue scale (VAS); and pulp vitality assessment, using palpation, cold, percussion, and EPT tests, will be completed. Data will be collected in a form (attachments #7) and inputted into a secure, web-based Research Electronic Data Capture (REDCap) application.
- **Clinical intervention:** As for any dental appointment for caries removal, the patient's medical history will be reviewed, vital signs will be taken, and standard procedures for caries removal and restoration will be done. These include local anesthesia and rubber

dam isolation. The caries will be accessed aseptically with conventional burs and high speed hand piece instruments.

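### The draw is attached to screening approval, before the direct/indirect stratum can be reliably known, and no rule covers a tooth whose stratum changes after the draw

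*Combined protocol and SAP*

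**What the plan says.** Subject management and recruitment process is the only section that gives the draw a time point: "Once patients have been properly screened and approved for the study, the selection of the treatment that they will receive will be carried out" at random. It then sets an order: "Teeth of subjects will be first stratified into those needing indirect pulp capping and direct pulp capping". The number of arms follows from that sorting: "Based on stratification, subjects will be randomized to one of three arms (indirect pulp capping) or one of two arms (direct pulp capping").

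Under Study schedule, the screening item says what approval rests on: "potential subjects will be approved after a thorough interview and intraoral and x-ray examinations". Caries removal belongs to the later clinical intervention item.

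The Radiographic inclusion criteria describe every eligible tooth in two ways: "Extension of carious lesion close to potential exposure upon excavation", and "with the presence of a well-defined radiodense zone between the lesion and the pulp".

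The clinical intervention text calls its opening steps common to both therapies, and only afterwards mentions that protocols are randomized. It states that protocol C is not indicated for direct capping. The visit summary that closes the Study schedule mentions random assignment after describing the intervention visit, without giving a time. The Statistical Analysis Plan computes success rates separately for indirect and direct therapies and names no analysis population.

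**The concern.** The stratum decides whether a tooth can be drawn to three arms or two, so it has to be settled before the draw. The feature that appears to separate the strata, pulp exposure, is seen only when caries is removed. A team that follows the recruitment section as written would sort and draw at approval, on radiographs and clinical examination alone.

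Three things would then be at stake:

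- A tooth sorted as indirect, drawn to C and later found to need direct capping has no place in the direct comparison of A with B. The plan does not say whether it is dropped, redrawn, moved or kept where it was.
- Each stratum is analysed on its own. Who belongs to it would depend on something that happens after randomization, so the groups compared would no longer be exactly the groups randomized.
- An operator who already knew the arm could, even unintentionally, affect whether a tooth ends up exposed. This is a possibility only; nothing in the documents shows that it happens.

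**Working it through.** **1. No figure to reproduce.** The plan gives 150 teeth, with no power calculation, split by stratum, exposure rate or allocation ratio. The check is therefore a comparison of passages, followed by an illustration on stated assumptions.

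**2. The passages side by side.**

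- *Recruitment section:* selection comes once patients are approved; stratify, then draw.
- *Screening item:* approval uses interview, mouth and x-ray examination. No excavation has taken place.
- *Radiographic criteria:* all eligible teeth show a dense zone over the pulp, and exposure is only a possibility on excavation. These findings cannot reliably separate direct from indirect teeth.
- *Clinical intervention item:* "standard procedures for caries removal and restoration will be done", then "The caries will be accessed aseptically with conventional burs and high speed hand piece instruments", then the remark that these steps are shared, then randomization. This order fits a chairside draw. It does not establish one, because the first sentence also covers restoration, and the last step described is access to the caries, not completed excavation or a check for exposure.
- *Visit summary:* no time given.

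The documents therefore leave open whether the draw comes before or after exposure status is known. On either reading there is no stratum criterion and no rule for a change of stratum.

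**3. Illustration if the draw is made at approval.** Assumptions, none of them in the documents: a fraction *e* of the 150 teeth needs direct capping; early sorting catches a fraction *s* of these; the indirect draw is 1:1:1; teeth are independent.

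- Direct teeth found late = 150 × e × (1 − s).
- Of these, holding C = one third = 50 × e × (1 − s).
- Chance of at least one = 1 − (1 − e(1 − s)/3)^150.

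At e = 5%:

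- s = 50%: 50 × 0.05 × 0.50 = 1.25 teeth; chance 1 − (1 − 0.025/3)^150 = 0.715.
- s = 75%: 50 × 0.05 × 0.25 = 0.625 teeth; chance 1 − (1 − 0.0125/3)^150 = 0.465.

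Expected conflicting C teeth over a range of e:

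| e | s = 50% | s = 75% |
|---|---|---|
| 5% | 1.25 | 0.6 |
| 10% | 2.5 | 1.25 |
| 20% | 5 | 2.5 |
| 30% | 7.5 | 3.75 |

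**4. Possible bias in the indirect comparison.** Let e2 = e(1 − s)/(1 − es) be the exposure rate among teeth sorted as indirect. Suppose that knowing the arm leads to a fraction f of exposures in C being avoided, and that those teeth succeed 70% of the time against 90% for the rest. The shift in C is 20 × f·e2 / ((1 − e2) + f·e2) points.

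- With f = 0.5, e = 5%: 0.26 points (s = 50%) or 0.13 points (s = 75%).
- With f = 0.5, e = 30%: 1.94 or 1.02 points.
- With f = 0, that is, excavation independent of arm: 0.

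For scale, the 95% half-width for a difference between two arms at 90% success is 1.96 × √(2 × 0.9 × 0.1 / n). This is 11.8 points at n = 50 and 14.1 points at n = 35 teeth per arm.

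**5. If the draw follows the exposure check,** every quantity in steps 3 and 4 is zero.

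**The case against.** The strongest reply is that the harmful reading is not the natural one. Attaching the draw to approval can be taken as setting an earliest moment, not a visit. The text insists on stratifying first. If the stratum cannot be known at screening, that instruction makes best sense at the chair, which is also where the clinical intervention item mentions randomization. This stands to the extent that a reader who infers that the trial does randomize before excavation goes further than the documents allow. It does not close the gap: the only stated time point is still approval, and neither later passage overrides it.

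A reader might also infer that one third of all direct teeth would end up holding C. That needs early sorting to catch no direct tooth at all, in which case the two-arm direct draw would never occur. Such a plan is not the one described, so that figure should not be used.

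Two further points stand. That direct capping means capping an exposed pulp is an inference from the radiographic criteria and the exclusion of C; the documents never define it, and the missing definition is part of the same gap. And every magnitude above is assumed. A reader who concludes that the results would be materially biased has no support for it here.

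**Conclusion.** The concern holds as a conflict over timing and a missing rule. The recruitment section, followed as written, sorts and draws teeth before the feature that appears to define the strata has been observed. The Study schedule permits a later draw without fixing it. Nothing says how to count a tooth whose stratum changes.

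The size is unknown, and is zero if the draw already follows the exposure check. If it does not, then with 5% of teeth needing direct capping and 50-75% of them caught early, about 0.6 to 1.25 conflicting C teeth are expected, with a 46.5% to 71.5% chance of at least one. Any bias in the indirect comparison is probably small beside a half-width of 12 to 14 points. What is gained is a clear definition of who is in each comparison, not the removal of a large bias. It should be fixed, with moderate confidence, because the repair is cheap.

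**What to change.** Reconcile the recruitment section, the clinical intervention item and the visit summary so that they describe one sequence:

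1. Define the direct and indirect strata in the protocol.
2. Record the stratum at the intervention visit once exposure status is known.
3. Only then open the next concealed allocation for that stratum from a pre-generated list, in REDCap (already in use) or sealed envelopes: three arms for indirect, two for direct.
4. State in the Statistical Analysis Plan that each tooth is analysed in the stratum and arm recorded at that point, and that any tooth whose exposure status changes afterwards is reported by arm.

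How an exposed tooth is managed clinically is left to the investigators.

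The cost is one protocol paragraph, a sentence in the analysis plan and two lists, with no extra teeth, visits or staff. The practical downside is that materials for all arms must be ready chairside and the allocation is opened during the procedure. If the team already works this way, the change only writes it down.

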### **Clinical Protocol: Operators' calibration**

The study will be carried out in the UIC College of Dentistry, Clinical Research Center. The investigators will be calibrated for case selection using bitewing and periapical radiographs representing different lesion depths. Initial radiographs will be evaluated independently for root maturity, bridge formation, and periradicular status by two examiners blinded to the technique, with forced consensus in cases of disagreement.

All restorative procedures will be performed by three calibrated clinicians, who will use the 3 different lining/sealers materials in equally distributed subjects.

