- These preliminary procedures will be the same for direct and indirect pulp capping therapies. Three restorative protocols will be investigated in indirect pulp capping cases (see below protocols A, B, C) and two restorative protocols will be investigated for direct pulp capping (see below: protocol A and B). The protocol C is not indicated for direct pulp capping.
- Treatment protocols will be randomized and the subjects will be treated as follow:
  - o Protocol A: Use of an intermediate layer of TheraCal LC between cavity floor and adhesive system/resin composite. Theracal LC will be applied directly to the cavity floor in increments of 1mm thickness. The layer will be light cured for 20 seconds, as recommended by the manufacturer's instructions.
  - o Protocol B: Use of an intermediate layer of Dycal between cavity floor and adhesive systems/resin composite. Base and accelerator pastes will be equally dispensed, mixed, and immediately applied at the deepest portion of the preparation following manufacturers instructions. A thin layer of conventional glass ionomer (Vitrebond – 3M ESPE) will be applied over the Dycal and light cured for 30s as recommended by the manufacturer.
  - o Protocol C: No placement of an intermediate material between cavity floor and adhesive system/resin composite.
- Following the above procedure, every tooth, regardless of the above protocol, will be restored following the traditional steps for resin composite restorations. The remaining enamel of the cavity wall will be selectively etched with Bisco's Select HV Etch. The acid will be rinsed thoroughly and excess water will be removed with high suction and/ or cotton pellets leaving the preparation visibly moist. Two separate coats of adhesive (All-Bond Universal) will be scrubbed into the preparation with a microbrush for 10-15 seconds per coat. The excess solvent will be evaporated and the adhesive will be light cured for 20 seconds.

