All subjects will attend the College of Dentistry for a total of 5 times of approximately 1-2 hours each in a one year period for an approximate 6 hours. There will be a screening appointment for data collection and review inclusion and exclusion criteria for subject selection. The next appointment will be the intervention, where the patient's decayed tooth selected for the study, will be treated and restored. Treatment will be randomly assigned to each subject. The 3, 6 and 12 months appointments will be follow up appointments for data collection. (See above for further details of each appointment). On each appointment, medical history will be updated and oral examination will be performed.

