### **Data handling and Interpretation**

Data entry and database management will be done in an ongoing manner by project staff. All data will be entered in a timely manner once collected. The database will be password protected and housed in a secure location. The database will be backed up on a regular schedule with backup copies stored in a separate location from the primary file server. Quality of data entry will be enhanced by double entry data forms with field and range validation. Project management tools include graphical interfaces for tracking timeliness of data entry, missing data, graphical reports of actual recruitment versus recruitment goals on a real-time basis (i.e., updated as each participant is entered into the system), and other reports. The goal is 100% data accuracy.

Data and/or information which identifies the subject and the signed consent form may be looked at and/or copied for evaluation of the research protocol by: UIC Office for the Protection of Research Subjects, State of Illinois Auditors, State of Illinois Auditors and the research sponsor (Bisco Dental Products).

**Statistical Analysis Plan:** Descriptive data and rates of success will be calculated independently for indirect and direct therapies. Statistical analyses of proportions will be done using Fisher's test and 95% confidence intervals (CI).

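### Does the stated balance of materials across three clinicians need a randomisation rule to secure it?

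*Combined protocol and SAP*

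**What the plan says.** The sentence at issue is in Clinical Protocol: Operators' calibration. Three calibrated clinicians do all the restorations, "who will use the 3 different lining/sealers materials in equally distributed subjects".

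Allocation is described in Subject management and recruitment process. After screening, "the selection of the treatment that they will receive will be carried out randomly, using random integer generator". One stratification factor is named: "Teeth of subjects will be first stratified into those needing indirect pulp capping and direct pulp capping". Indirect cases go to one of three arms and direct cases to one of two.

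Study schedule adds "Treatment will be randomly assigned to each subject" and, on the third protocol, "The protocol C is not indicated for direct pulp capping". The sample size in Study Protocol is "150 teeth with deep caries of subjects willing and able to return", with no split by capping type, arm or clinician. The analysis in Data handling and Interpretation is Fisher's test with 95% confidence intervals, separately for indirect and direct therapy, with no clinician term.

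**The concern.** The calibration sentence states a result, and the allocation text does not say how it is reached. The sentence can mean three things: each clinician uses the materials equally often, the clinicians carry equal caseloads, or the materials are used equally often overall. Nothing in the documents guarantees any of the three. Clinician is not a stratum, no booking rule is given, and integers drawn one tooth at a time do not force equal arms. Direct cases can receive only A or B, so totals pooled over capping type would lean away from C even on average.

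If clinicians differ in skill and one of them happens to place more of one material, part of an observed difference between materials would reflect the operator. The planned analysis does not adjust for that.

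**Working it through.** **Inputs.** From the documents: 150 teeth, three clinicians, three indirect arms, two direct arms. Assumed, because the documents do not say: independent draws with equal probabilities, about 100 indirect and 50 direct teeth, an even split between clinicians (33 indirect, 16 or 17 direct each), clinician assigned independently of arm, and the success rates below. The protocol gives no figure for balance that could be reproduced.

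**1. How uneven could the counts be?** For n teeth drawn over three arms, the difference between two arm counts has SD √(2n/3).

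- One clinician, n = 33: SD = √22 = 4.69. A gap of 8 or more between A and B has probability of about 2·P(Z > 7.5/4.69) = 0.11. Simulation gives 0.109. For any pair of arms it is 0.25, and for any pair in at least one of the three clinicians 0.58.
- All indirect teeth, n = 99: SD = √66 = 8.12. A gap of 10 or more between A and B has probability of about 2·P(Z > 9.5/8.12) = 0.24. Between the largest and smallest arm it is 0.47 by simulation.
- Direct teeth, one clinician: a gap of 6 or more has probability 2·P(X ≤ 5) = 0.21 for X ~ Bin(16, ½), and 0.14 for Bin(17, ½).

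Uneven counts are therefore quite likely under independent draws. The question is what they do to the result.

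**2. Shift in the A–B difference, indirect.** The shift is the difference between the two arms' success rates when each is averaged over its own clinician mix. Its mean is 0. With about 33 teeth per arm its SD is about √(2V/33), where V is the variance of the three clinician rates. The median absolute shift is about 0.67 SD and the 95th percentile about 1.96 SD.

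| Clinician rates (%) | V | SD (points) | Median / 95th percentile, formula | Simulated |
|---|---|---|---|---|
| 95, 90, 80 | 38.9 | 1.54 | 1.0 / 3.0 | 1.1 / 3.1 |
| 95, 90, 85 | 16.7 | 1.01 | 0.7 / 2.0 | 0.7 / 2.0 |
| 92, 90, 88 | 2.7 | 0.40 | 0.3 / 0.8 | 0.3 / 0.8 |

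**3. Compared with the planned interval.** At 90% success and 33 per arm, SE = √(2 × 0.9 × 0.1/33) = 7.4 points, and the half-width is 1.96 × 7.4 = 14.5 points.

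The binomial variance p(1−p) already contains the between-clinician part V. At 95/90/80% the mean is 88.3%, so p(1−p) = 0.1031 and V = 0.0039, a share of 3.8%. Removing V entirely changes the half-width from 1.96·√(2 × 0.1031/33) = 15.5 points to 1.96·√(2 × 0.0992/33) = 15.2 points. That 0.3 points is the most that balancing on clinician could gain in the widest of the three scenarios.

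**4. Cost of unequal arm totals.** With all 150 teeth indirect and assumed success of 90% against 70%, normal-approximation power is 71.1% at 50 and 50 teeth and 68.5% at 42 and 58.

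**5. Cost of forcing the balance.** Permuted blocks within clinician and capping type (sizes 3 and 6 for indirect, 2 and 4 for direct) hold the within-clinician gap to 2 teeth. They cut the 95/90/80% shift to a median of 0 and a 95th percentile of 0.5 points. An operator who follows their own list and guesses the least-used arm would be right about 57 to 58% of the time for indirect cases instead of 33%, and 71% for direct cases instead of 50%.

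**The case for a change.** The best case for a change is that the sponsor wrote this balance into its own protocol, so either the method should deliver it or the sentence should go. The documents also do not say that the treating clinician will be recorded, and without that nobody could check later whether the balance was met. A remedy looks cheap: six short lists in a data system already in use, or a line of rewording.

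The textual point stands: the mechanism is not stated. Three things limit it.

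- The documents do not say whether integers are drawn tooth by tooth or used to build a list, so the counts in step 1 describe one possible reading only. Equal caseloads can be met by ordinary booking and need no randomisation rule.
- The mention of three materials misleads nobody about direct capping, because the recruitment and schedule sections both set out two arms there.
- The lists are cheap to make but not free of risk. The three protocols differ visibly at the chair, so the operator knows what was placed. Fixing eligibility, clinician and capping type before the arm is revealed limits the use of a good guess but does not remove it. That would exchange a chance imbalance with zero expected bias for some risk of selection.

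Rewording the sentence, or noting the clinician on the form, would be tidy but would change no planned result.

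**Conclusion.** No change to the plan follows. The calibration sentence states an aim whose mechanism is left open, and study staff can fill that gap sensibly. The consequence is at most a chance difference in clinician mix. Under the assumptions listed, it shifts an indirect comparison by a median of 0.3 to 1.1 points, with a 95th percentile of about 3 points in the widest scenario, against a half-width of about 15 points. Fisher's test and its interval remain valid, and the interval already carries this variation. Simple randomisation within capping type is a fair choice, and small blocks within clinician would buy very little at a real cost in predictability.

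This rests on clinicians being assigned independently of arm. Nothing in the documents suggests otherwise, and the sentence itself has every clinician using the different materials. The 100/50 split and the success rates are illustrative. Clinicians would have to differ by much more than 15 points in success for the conclusion to change.
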